## 7F. Narratively describe the research procedures in the order in which they will be conducted.

1. Phone Pre-Screening: All participants will undergo a phone screening to determine initial eligibility for the next step (video screening). The phone screening will gather information about basic demographics, living arrangements, and visual and auditory acuity. TICS-M will be administered to screen for global cognition. Participants who meet the initial eligibility criteria will be invited to participate in a video screening.
2. Informed Consent for Video Screening: Electronic informed consent will be obtained from all participants using REDCap to participate in a screening session over videochat. The participants with MCI will have no deficits in global cognitive functioning, as determined by TICS-M. Subtle cognitive changes observed in these individuals do not impact their ability to provide informed consent; therefore, no proxy consent will be required.
3. Video Screening: After obtaining online informed consent, participants will complete a background questionnaire (TSBQ). The Montreal Cognitive Assessment (MoCA) will be administered to assess global cognition. The Geriatric Depression Scale (GDS) will be administered to screen for elevated depressive symptoms. Researchers will review and determine final eligibility for participation. Those who meet eligibility will be invited to participate in the study. If they agree to participate, they will be consented for the intervention study before administering baseline assessment. If a participant does not qualify or prefers not

to participate despite being eligible, they will be thanked for their participation. The session will last approximately 45 minutes. All participants regardless of eligibility will be paid \$15 for the video screening session.

4. Informed Consent for RCT: Electronic informed consent will be obtained from all participants using REDCap for the RCT. Details about the study, expectations, risks, and benefits will be described. All questions will be clarified, and comprehension of the information will be checked by using the teach-back approach. The participants with MCI will have no deficits in global cognitive functioning. Subtle cognitive changes observed in these individuals do not impact their ability to provide informed consent; therefore, no proxy consent will be required.

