5. Baseline Assessment: Baseline assessment will include participant characterization measures and intervention outcome measures. The session will last approximately one hour.
6. Randomization process: The randomization process is designed to achieve appropriate generation of the random allocation sequence and concealment of the allocation sequence. A researcher who is not involved in phone screening, video screening, or informed consent will generate the randomization list prior to the screening of the first person for the randomized, controlled trial. The randomization list will use computer-generated random numbers. The randomization list will be stratified with random permuted blocks. The stratification variable will be Mild Cognitive Impairment (MCI present versus absent). MCI will be defined by a MoCA score of 20-25. The block size will vary randomly between 4 and 6. Research personnel who perform phone screening, video screening, informed consent, or assessments will not be able to access the randomization list. After a potential participant has completed phone screening and video screening, has fulfilled all inclusion criteria, has demonstrated no exclusion criteria, has provided documented informed consent, and has completed baseline assessment, the researcher will unconceal the randomization assignment for the intervention: Group 1 (intervention first) versus Group 2 (intervention later). After assignment, the participant and the researcher who performed informed consent will not be blinded to group allocation.
7. Participants in Group 2 will be told they will begin the intervention 8 weeks later and in the meantime will be asked to complete assessments at 4 and 8 weeks after joining the study but before beginning the video chat participation. Participants in Group 1 will be given information about the general research expectations over the next 8 weeks and will be invited to sign up for a technology training session to learn how to use the OneClick system.

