**14B. List all researchers who will obtain consent/assent/parental permission from participants.**

[name], [name], [name], [name], [name] (For more information of the researchers, please see attached research team form).

**14C. Describe the method for obtaining consent/assent/parental permission.** Informed consent will be obtained online before any testing is undertaken. Details related to the study will be discussed at length. Any questions pertaining to the study and participation will be answered. The online informed consent process will be administered over REDCap with a research team member and signed electronically. Participants will receive a copy of the signed document for their records (either electronically or a paper version mailed to their home).

**14D. Describe when consent/assent/parental permission will be obtained.** Informed consent for the video screening will be obtained before the video screening session begins. Informed consent for the RCT will be obtained before the baseline assessment session begins.

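### Step 6 unblinds each consenting researcher and does not bar them from enrolling later participants, so the next allocation can be partly predicted before consent

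*Protocol*

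**What the plan says.** All of this is in the Protocol; the SAP does not discuss allocation.

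- **Sequence.** Section 7F, step 6: "The randomization list will be stratified with random permuted blocks". The only stratification variable is MCI, present or absent, so there are two strata and site is not one of them. On block length: "The block size will vary randomly between 4 and 6".
- **Protection of the list.** A researcher outside phone screening, video screening and consent generates it before the first person is screened. In addition: "Research personnel who perform phone screening, video screening, informed consent, or assessments will not be able to access the randomization list".
- **Timing of the reveal.** The assignment is opened only once the participant has been found eligible, has consented and "has completed baseline assessment, the researcher will unconceal the randomization assignment for the intervention". Step 6 does not say which researcher this is.
- **Who then knows.** "After assignment, the participant and the researcher who performed informed consent will not be blinded to group allocation".
- **What comes before assignment.** Section 7F, step 3: "Researchers will review and determine final eligibility for participation". The MoCA, which defines the stratum, is given at that video screening, so the stratum is known before consent to the RCT.
- **How many consenters.** Section 14B has five entries (names removed) for people who obtain consent. Section 9A plans 176 participants, 106 at UIUC and 70 at CJE.

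No passage says whether a consenter who has learned one allocation may consent later participants, or whether staff may tell each other assignments.

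**The concern.** Concealment has two parts: nobody who enrols can look up the next allocation, and nobody who enrols can work it out. Step 6 secures the first. The second is weakened because allocations within a block must balance. Someone who knows that recent participants in a stratum went mostly to one group knows that the other group is now more likely, without ever seeing the list. Step 6 supplies that knowledge to the consenter, one participant at a time, and the protocol states how short the blocks are.

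Revealing the current allocation after baseline prevents anyone from knowing it early. It does not prevent anyone from predicting it from earlier ones. What is at stake is selection at entry: a consenter who expects a particular group could, deliberately or not, press harder or less hard for consent, or time the consent differently. Groups that differ through such selection stay different under the SAP's intention-to-treat analysis, which keeps everyone in the group they were allocated to but cannot undo how they came to be allocated.

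**Working it through.** The documents give no predictability figure, so there is nothing to reproduce.

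**Inputs.** From the documents: two strata, random permuted blocks, size between 4 and 6, 176 planned participants, five consenters, two sites. Assumed: 1:1 allocation (not stated); block sizes 4 and 6 equally likely (a block of 5 cannot balance two equal arms); 88 per stratum, i.e. 176/2 (the split is not stated).

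**1. Upper bound: every earlier allocation in the stratum is seen.** The observer always guesses the arm that is behind, and tosses a coin when the arms are level. For a block of size 2k the expected number of correct guesses is k + (4^k / C(2k,k) − 1)/2.

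- Block of 4 (k = 2): 2 + (16/6 − 1)/2 = 2.833; 2.833/4 = 70.8%.
- Block of 6 (k = 3): 3 + (64/20 − 1)/2 = 4.1; 4.1/6 = 68.3%.
- Equal mix, realised sizes known: (2.833 + 4.1)/10 = 69.3%.
- Equal mix, realised sizes not known, simulated with 88 per stratum: 69.1%. Strata of 44 or 132 give 69.0% and 69.2%, so the assumed stratum size hardly matters.

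**2. What the random block size achieves.** It barely changes the average (69.3% against 69.1%). It does reduce the allocations that can be known with certainty, from 28.3% when realised sizes are known to 5.5% when they are not.

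**3. Partial view.** Step 6 unblinds only the person who consented that participant. With five consenters and two sites drawing on the same two lists, each sees a fraction of the sequence. Simulated with the same assumptions, with the observer seeing only a random share of the stratum:

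| Guessing rule | 20% seen | 60% seen |
|---|---|---|
| Arm that is behind among own participants | about 52% | about 54% |
| Opposite of own last participant in the stratum | about 54% | about 58% |

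The 20% share corresponds to one of five consenters working equally. The 60% share corresponds to all of the larger site (106/176 = 60%). Neither rule needs to know when colleagues enrol. An observer who also knew when others enrolled, though not their groups, could reach 54.5% at a 20% share and 60.1% at a 60% share; the documents do not say that consenters have this information.

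**4. Reading.** Against 50 correct guesses per 100 by chance, partial view gives roughly 2 to 8 more and full view about 19 more.

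**The case against.** The strongest reply is that the protocol does not create the well-informed observer. Five people obtain consent, two sites share lists that are not stratified by site, and each person is told only about their own participants. This stands: a reader might infer that about 69% is the typical hit rate, but it needs one person to see all of a stratum's allocations, or staff to pool them, which the documents neither describe nor forbid.

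A second reply is that existing safeguards leave little room to act on a guess. The list is generated independently and is inaccessible, block size varies, the reveal follows eligibility, consent and baseline, and the main eligibility limits in Section 10A are numeric scores. Both groups eventually receive the intervention, which weakens any motive to steer. These points reduce the risk. They do not close the consent conversation, which the consenter conducts by definition, and Section 10A also contains criteria that need judgement, such as adequate acuity and absence of significant functional impairment.

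A third reply concerns roles. A reader might infer that the consenter also screens, decides eligibility or runs baseline, or that unblinding consenters depletes the supply of blinded week-4 and week-8 assessors. The documents say none of this. Step 6 lists screening, consent and assessment as separate tasks without saying who overlaps, and step 10 already requires a blinded assessor. Those claims are not made here.

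Finally, the participant in a wait-list design must know the group. That is true, but it gives no reason for the consenter to know it.

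**Conclusion.** The gap is real but modest. Step 6 protects the list and then gives consenters the information from which the next allocation can be partly inferred, with no rule separating those who know past allocations from those who enrol next. The likely size is about 52% to 58% correct guesses for a consenter who sees 20% to 60% of a stratum, depending on the guessing rule, with about 69% as the ceiling. This rests on 1:1 allocation, blocks of 4 or 6 in equal proportion and 88 per stratum.

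It would go too far to conclude that concealment has failed or that the treatment comparison is biased by a known amount. The documents show an opportunity for selection, not its use, and nothing in them turns a hit rate into a bias in an outcome. The point is a low-cost improvement to a stated rule.

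**What to change.** Replace the last sentence of step 6 so that it says three things:

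1. The participant learns the allocation from existing staff who neither obtain consent nor determine eligibility, for example the list holder or the technology trainer.
2. Staff who obtain consent or determine eligibility are not told allocations.
3. Assignments are not shared with those staff by colleagues at either site.

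Also move the block sizes from the protocol to a document that enrolling staff do not hold. On its own this does little for average predictability, as the 69.3% and 69.1% figures show; its use is to reduce near-certain guesses. The separation of roles does most of the work.

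The cost is a wording change and one hand-off call or message per participant. It assumes that each site has someone outside consent and eligibility who can make that contact. The documents do not set out staffing in enough detail to confirm this, although step 10 already provides for a separate unblinded interviewer. If people have already been enrolled under the present wording, record who consented whom and who knew earlier assignments, so that the exposure can be reported.

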# Protocol Form

unable to do so with remote instruction. During the training participants will also be provided with an opportunity to RSVP for OneClick video chat events.

9. OneClick social engagement intervention: At least two days before starting the intervention, participants will receive a reminder call/email about RSVPing for the OneClick video chat session. If they have not, we will invite them to do so while the researcher is on the phone, in case of difficulties. Participants will receive an email or telephone reminder(s) about the event topic options for the upcoming week and encouraged to sign up for the ones that are of interest to them (no more than 3 reminders will be sent). We will ensure there are at least five unique events that cover a range of topics each week. Each event will last approximately 45 minutes. The event will begin with an introduction to the topic and a set of initial idea for discussion related to the topic. Events include a variety of topics, based on research from a previous study. These topics include arts and culture; nature, health, and wellness; life experiences; science and technology; and recreation and sports. All events include a series of pictures and discussion questions which have been designed to be positive and require a low memory load. Each event will involve a minimum of 3-4 individuals. If an event is not attended by a minimum of 3 participants, we will have a pool of volunteers to join the event who are knowledgeable or interested in the topics to ensure the minimum group size for each event is maintained. Events will be open only to research participants and trained volunteers to ensure a safe and controlled environment for everyone at this stage of product testing and development. During the intervention, we will measure frequency of use, topic selection, discussion duration, and feedback comments/ratings after each event. (i.e. enjoyment, ease of use, quality of video and audio). If participants have not attended an event over the span of a week they will be contacted via their preferred method of communication to remind them to sign up for at least 2 events per week. Participants will be contacted for up to three weeks. If no contact has been made for three weeks, the participant will be dropped from the study and informed via their preferred method of communication.
10. Week-4 assessment: 4 weeks after being placed into Group 1 or Group 2, participants will be contacted to schedule a week-4 assessment. Participants in both groups will complete measures related to social connectedness, loneliness, isolation, and quality of life. Group 1 will additionally complete measures related to system usability and perceived enjoyment of the OneClick system. This assessment session will take approximately 1 hour will be administered by a blinded assessor remotely over video or phone. Participants will be informed at the beginning of the assessment not to reveal their group assignment. Both groups will receive \$25 for this session. For Group 1 only, an additional short, semi-structured interview will be administered over video or phone by an unblinded assessor. This will focus on ease of use, usefulness, enjoyment, satisfaction with the topics and conversation, suggestions for updates, and perceptions of social connectedness and will take 30-45 minutes. The interviews will be audiotaped and transcribed verbatim. Group 1 will receive \$15 for completing the interview.

11. After this week-4 assessment, a research team member will contact participants in Group 1 to address any questions and issues related to the intervention to help participants remain engaged in the next 4-weeks of intervention.
12. Week-8 assessment: 8 weeks after being placed into Group 1 or Group 2, participants will be contacted to schedule a week-8 assessment. Each group's assessment sessions and compensation will be identical to week-4 assessment. This ends Group 1 participation in the study. They will receive a study debriefing and thanked for their time.
13. After the week-8 assessment, a research team member will contact participants in Group 2 to schedule their technology training session (described in step #8).
14. Group 2 will now begin 8 weeks of video-chat intervention
15. Four weeks after completing video chat participation, Group 2 will complete another assessment. Participants will complete measures related to social connectedness, loneliness, isolation, quality of life, system usability, and perceived enjoyment of the OneClick system. This assessment session will take approximately 1 hour and participants will receive \$25. An additional short, semi-structured interview will be completed over video or phone. This will focus on ease of use, usefulness, enjoyment, satisfaction with the topics and conversation, suggestions for updates, and perceptions of social connectedness and will take 30-45 minutes. The interviews will be audiotaped and transcribed verbatim. Group 2 will receive an additional \$15 for completing the interview. Assessors will no longer be blinded to group assignment.
16. Following this assessment, a research team member will contact participants in Group 2 to address any questions and issues related to the intervention to help participants remain engaged in the next 4-weeks of intervention.
17. Eight weeks after beginning video chat participation, Group 2 will complete the final assessment. This assessment will follow the exact same procedures and compensation as the assessment done after completing 4 weeks of video chat participation (#15). Group 2 will now end study. They will receive a study debriefing and thanked for their time.

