**7B. List all testing instruments, surveys, interview guides, etc. that will be used in this research.**

Telephone screening DRAFT  
Modified Telephone Interview for Cognitive Status (TICS-M)  
Modified Techsage Background Questionnaire (TBSQ)  
Montreal Cognitive Assessment (MoCA)  
Geriatric Depression Scale (GDS)  
Instrumental Activities of Daily Living (IADL)  
Mobile Device Proficiency Questionnaire (MDPQ-16)  
Computer Proficiency Questionnaire (CPQ)  
Logical Memory  
Friendship Scale  
UCLA Loneliness Scale- Version 3  
Quality of Life- AD  
System Usability Scale  
Perceived Ease of Use and Usefulness  
Interpersonal Support Evaluation List  
Intention Survey  
Lubben Social Network Index  
Session Feedback Questions DRAFT  
Opinion Interview DRAFT  
Category Fluency  
Social Activity Frequency (SAQ)

**Drafts or final copies of all research materials are attached.**  Yes

**7C. List approximate study dates.** Date of IRB approval- August 1, 2024

**7D. What is the duration of participants' involvement?** Participants' eligibility will be determined following a phone pre-screening and a video screening. If eligible, participants will be randomized into an

immediate social engagement intervention group or a later intervention group after a 1-hour baseline assessment.

**Group 1 (intervention first):** Participants in this group will receive 8 weeks of the OneClick social engagement intervention. During this 8-week period, they will be asked to participate in 2 social engagement intervention sessions per week each lasting approximately 45 minutes. A mid-assessment will be done 4 weeks after the beginning of the intervention, and a final post-assessment after 8-weeks of intervention. Both assessments will take 1 hour. Participants will additionally complete a 30-45 minute phone interview at 4 and 8 weeks.

**Group 2 (intervention later):** After being placed in Group 2, participants will receive no planned intervention in the first 8 weeks. They will complete one assessment after 4 weeks and another after 8 weeks. Both sessions will last 1 hour. Then participants will be rolled into the OneClick social engagement intervention lasting 8 weeks. They will complete two additional assessments, one 4 weeks and the other 8 weeks after beginning the video chat intervention. These assessments will last 1 hour. Participants will additionally complete a 30-45 minute phone interview at 12 and 16 weeks.

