**12B. Select all forms of remuneration that apply.**

Cash, please specify amount:

Check, please specify amount:

Gift Certificate, please specify amount: All participants who complete a video screening session will receive \$15 Amazon e-code. To promote the highest retention rate possible in the RCT, participants will be compensated \$25 at each assessment session. There is an additional supplemental interview that will be given to participants currently receiving the intervention and they will be paid \$15 for each supplemental interview. Although participants in Group 2 will complete two additional assessments

(week-12 and week-16), they will be compensated for these two additional assessments. Also, participants will be allowed to keep their OneClick subscription for a year free of cost.

Lottery, please specify amount: and odds:  
 Course Credit, please specify amount: and specify equivalent alternative activity:  
 Other, please specify: Amazon e-codes will be the primary form of payment, but participants can request an alternative method (cash or check).

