Identifiers: NCT05380180

Brief Title: Enhancing Quality of Life for Older Adults With and Without Mild Cognitive Impairment (MCI) Through Social Engagement Over Video Technology

Document Date: Sept 4, 2023

Statistical Analysis Plan

To measure the main effects of the intervention on primary and secondary outcomes, irrespective of the cognitive status, the OneClick intervention Group will be compared to the Waitlist group at (i) mid-assessment (4 weeks) compared with the baseline assessment, and (ii) post-assessment (8 weeks) compared with baseline assessment. In addition, we will perform a separate analysis of covariance with age and cognitive ability (MoCA and Logical Memory - Delayed Recall) as covariates. We plan to implement an intent-to-treat analysis where all participants who were allocated to either the intervention or waitlist group will be included in the analysis, regardless of the number of sessions attended or their completion of assessments.

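### Unreachable non-attenders are dropped from the study, a rule only Group 1 can meet before week 8, and no method is given for including them in the all-allocated analysis

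*Protocol*

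**What the plan says.** **The rule.** Protocol Section 7F, step 9 describes the intervention period. The trigger is non-attendance: "If participants have not attended an event over the span of a week they will be contacted via their preferred method of communication". The contact period is limited: "Participants will be contacted for up to three weeks". Then: "If no contact has been made for three weeks, the participant will be dropped from the study". A non-attender who replies is not dropped.

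**Who is exposed.** For Group 2, Section 7D says "participants will receive no planned intervention in the first 8 weeks". Section 7F, step 13 schedules Group 2's technology training only after its week-8 assessment. No corresponding drop rule is given for the waiting period.

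**The assessments.** Section 7F, step 12 covers both arms: "8 weeks after being placed into Group 1 or Group 2, participants will be contacted to schedule a week-8 assessment". It makes no provision for people already dropped. Section 12B pays for each assessment, with the stated aim "To promote the highest retention rate possible in the RCT".

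**The analysis.** The SAP compares the arms at 4 and 8 weeks against baseline and adds a separate analysis of covariance with age and cognitive measures. It commits to an intent-to-treat analysis of everyone allocated, "regardless of the number of sessions attended or their completion of assessments". It names no model for the main comparison, no missing-data method and no sensitivity analysis. The protocol supplies none either.

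**The concern.** Stopping the intervention and leaving the study are different events. An intent-to-treat comparison needs outcomes from people who stop taking part in sessions. Step 9, on its plain reading, stops collecting them.

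The rule acts on one arm and is triggered by behaviour after randomisation. If the people removed differ in outcome from those who stay, Group 1 loses them while similar people in Group 2 remain, and the week-8 comparison is no longer between the groups as randomised.

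The direction cannot be predicted. Unreachable people may be more isolated, in which case losing them favours OneClick. They may instead be busy and well connected, in which case losing them works against it.

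The SAP says who is analysed. It does not say how a person with no week-8 outcome enters the analysis. It does not commit to a completers analysis, but a reader cannot tell what will be done instead.

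**Working it through.** **Step 1. Can the rule operate in both arms before week 8?** The trigger is a week without attending an event. Group 1 has events from the start of its intervention. Group 2 has none until after its week-8 assessment. Before that point only Group 1 can meet the rule.

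**Step 2. Which assessment is exposed?** Three weeks without contact, counted with or without the first missed week, puts the earliest drop at about week 3-4 of the intervention. Step 10 contacts participants 4 weeks after placement, and Group 1 has technology training before its first event, so week 4 is barely exposed. Week 8 is exposed.

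**Step 3. How large could the effect be?** There is no planned figure to reproduce. The protocol gives an enrolment goal of 176 (Section 9A) but no alpha, power, SD or dropout rate. What follows is an illustration.

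Inputs, all assumed except the total:
- 88 per arm (176/2, taking 1:1 allocation), SD 1, true effect zero, two-sided 5% test, normal approximation
- p: fraction of Group 1 dropped, all missing at week 8
- g: outcome gap in SD between such people and the rest, in either direction
- f: fraction of similar Group 2 people who are assessed
- r: correlation of baseline with week 8, where baseline is adjusted for

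Formulas:
- n1 = 88(1 - p); n2 = 88(1 - p + pf)
- bias = g × pf/(1 - p + pf); SE = √(1/n1 + 1/n2)
- with baseline adjustment and a gap that is stable from baseline, g becomes g(1 - r) and the SD becomes √(1 - r²)
- type I error = Φ(bias/SE - 1.96) + Φ(-bias/SE - 1.96)

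One case in full, p = 0.20, g = 0.5, f = 1, unadjusted: n1 = 70.4, n2 = 88, bias = 0.5 × 0.20 = 0.100 SD, SE = √(1/70.4 + 1/88) = 0.160, ratio 0.625, type I error 9.6%. With r = 0.7 the bias is 0.100 × 0.3 = 0.030 SD, the SE is 0.160 × 0.714 = 0.114, and the type I error is 5.8%.

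| p, g | Bias, f = 1, unadjusted | Type I error, f = 1, unadjusted | f = 0.5, unadjusted | f = 1, r = 0.7 |
|---|---|---|---|---|
| 5%, 0.25 | 0.013 SD | 5.1% | 5.0% | 5.0% |
| 10%, 0.3 | 0.030 SD | 5.4% | 5.1% | 5.1% |
| 20%, 0.5 | 0.100 SD | 9.6% | 6.3% | 5.8% |
| 20%, 0.8 | 0.160 SD | 17.0% | 8.4% | 7.0% |

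In the last row, f = 0.5 together with r = 0.7 gives 5.6%. The third column is an upper bound for each pair of p and g. A stable gap cancels completely in a pure change-from-baseline comparison. A gap that opens after randomisation does not, and is not modelled here.

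**The case against.** The case for leaving this alone is that the rule itself may cost few outcomes.

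- Someone who does not answer for three weeks through their own preferred channel may well not answer the week-8 invitation either. This stands, and the number lost to the rule alone is unknown. But ignoring reminders to sign up for events is not the same as declining a paid assessment, and a person told they have been dropped has no stated way back.
- The week-4 assessment and the follow-up call in step 11 are themselves contacts. On the natural reading, someone reached then needs a fresh three-week silence and could be dropped only from about week 7. Someone dropped between weeks 4 and 7 was probably missing at week 4 too. This narrows the window but does not close it.
- The larger figures use no baseline information, whereas the SAP compares with baseline. This is fair: the adjusted figures are closer to what the SAP describes, provided the gap is stable from baseline.
- What being dropped means is not defined, and Group 2 can lose people as well. Both are true. For that reason the claim is only that outcomes can go missing, and that the rule, not all missingness, differs by arm.
- The SAP's silence on missing data would remain if step 9 were rewritten. That is so, and it needs its own correction. It also means the analysis plan offers no stated protection against what step 9 creates.

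These points limit the size. They do not remove the conflict between a one-arm drop rule and a commitment to analyse everyone allocated.

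**Conclusion.** The concern holds and should be fixed. The reading of the text is secure: before week 8 the drop rule can act only in Group 1, and neither document says how people without week-8 data enter the promised analysis.

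The size is uncertain and probably modest. Under the assumptions above, the effect on type I error is negligible at 5-10% loss. It becomes material only if loss is near 20%, the gap is large and Group 2 is well retained, and baseline adjustment softens it when the gap is stable. The documents contain no attrition rate and no profile of non-responders, so the unfavourable case can be neither confirmed nor excluded, and no direction of bias is claimed. The reason to act is that the loss caused by the rule is avoidable and that analysis cannot recover outcomes never collected.

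**What to change.** 1. **Protocol Section 7F, step 9.** Replace the drop from the study with wording under which three weeks without contact ends the event reminders only. State that the participant is still invited to the week-4 and week-8 assessments on the same terms as Group 2, unless consent is withdrawn.
2. **SAP, main analysis.** Name a model that includes all randomised participants and uses baseline and all available follow-up, for example a repeated-measures model with arm-by-visit terms. Other methods could serve if specified in advance. Report losses by arm, visit and reason.
3. **SAP, sensitivity.** Such a model assumes data are missing at random. Add an analysis that shifts the missing Group 1 week-8 outcomes over a range, for example -0.8 to +0.8 SD, and report the shift at which the conclusion changes.

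The first change is worth making on its own.

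**Cost.** One protocol sentence, a few lines of SAP and some extra contact attempts. Payments are $25 per assessment, plus $15 if the Group 1 interview is also done. If 5-20% of 88 people (4.4 to 17.6, so about 4 to 18) are retained for week 8, that is 4.4 × $25 = $110 to 17.6 × $25 = $440, or at $40 each, $176 to $704. Any week-4 assessment retained in the same way adds the same amount per person.
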